This open-label, single-arm, Phase II multi-center study will investigate the activity, pharmacokinetics and safety of ruxolitinib added to the subject's immunosuppressive regimen among infants, children, and adolescents aged ≥ 28 days to < 18 years old with either moderate to severe treatment-naïve cGvHD or SR-cGvHD. Approximately 42 subjects will be enrolled in this study. Subjects will be grouped according to their age as follows: Group 1 includes subjects ≥ 12 y to < 18 y, Group 2 includes subjects ≥ 6 y to < 12 y, Group 3 includes subjects ≥ 2 y to < 6 y, and Group 4 includes subjects ≥ 28 days to < 2 y. Subjects will remain in the age group throughout the study based on the age at the time of start of treatment. Enrollment initiation into the youngest age group, Group 4, will be subject to the availability of data in this age group from study [CINC424F12201], as well as a review of available PK, safety, and activity data generated from Groups 1 to 3 in the current study, in consultation with the data monitoring committee (DMC) and a final decision by the Sponsor. At least 5 evaluable subjects per Group are needed for the primary analysis in Groups 1, 2 and 3. No minimum number of evaluable subjects are needed in Group 4.

[figure not shown]
After a screening period from Day -28 to Day -1, eligible subjects will begin the investigational treatment (ruxolitinib) on Cycle 1 Day 1 and will be treated for up to a maximum of 3 years (39 cycles/ 156 weeks) or until early discontinuation. Subjects who discontinue ruxolitinib for any reason earlier than 39 cycles will be followed every 6 months until 3 years from their first dose of ruxolitinib is reached. Refer to [Section 8.2.1](#) for details of the treatment period study visits. All subjects continuing to receive ruxolitinib treatment benefit following 3 years of treatment will be given the possibility to continue ruxolitinib outside the study, from another source, where permitted in accordance to local laws and regulations.

The ruxolitinib dose is based on the preliminary efficacy and safety data generated with this dose in subjects with steroid-refractory graft vs. host disease (SR-GvHD) ([Zeiser et al 2015](#)), and based on PK/safety data generated from the Phase III trials CINC424C2301 and CINC424D2301. As subjects ≥ 12 y to < 18 y are already being treated with 10 mg BID in CINC424D2301, this dose is the recommended phase II dose (RP2D), and will be used to treat all subjects in this age group.

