6.1.5 Treatment duration

The planned duration of study treatment is approximately 36 months (39 cycles).

The Treatment Period for each subject will begin on Cycle 1, Day 1 and continue until the end of Cycle 39 (Week 156), unless treatment change for any reason including treatment failure, e.g. cGvHD progression, mixed response or no response, or a GvHD flare as defined in [Section 6.1.5.2.1](#), intolerable toxicity, death, or withdrawal from the study for other reasons occurs.

During the Treatment period, the subjects' treatment will be managed according to their response as follows:

Subjects that achieve CR or PR: On Cycle 7 Day 1, subjects still receiving benefit from ruxolitinib may continue on ruxolitinib until the end of Cycle 39 (Week 156) and will follow the Visit Evaluation Schedule per [Table 8-1](#):

Subjects that achieve a CR or PR may taper corticosteroids at any time from two weeks of documented CR or PR. See [Section 6.1.5.2](#) for details

In subjects that achieve a CR or PR: A taper of ruxolitinib is allowed only on or after Cycle 7 Day 1.

- A taper of CNI is allowed after Cycle 7 Day 1.

Subjects who taper off ruxolitinib and all immunosuppressive therapy due to achieving a CR or PR will continue to follow the currently assigned Visit Evaluation Schedule ([Table 8-1](#)), including all safety and efficacy assessments, and will be monitored for cGvHD recurrence which must be reported in the database. Subjects experiencing cGvHD recurrence after tapering off ruxolitinib will be treated per Investigator discretion, which may include re-initiation of ruxolitinib and will follow the assigned Visit Evaluation Schedule ([Table 8-1](#)).

Subjects without CR or PR: If the subject is not receiving benefit from ruxolitinib therapy per investigator decision, the subject should discontinue ruxolitinib and be treated per institutional practice.

These subjects will enter the early discontinuation follow-up until completion of 39 cycles from their first dose of ruxolitinib.

Subjects who permanently discontinue ruxolitinib for reasons other than achieving a CR or PR prior to completion of 39 cycles on study will complete the safety follow-up visit and then follow the early discontinuation follow-up visit schedule (as described in [Table 8-1](#)). These subjects may be treated per Institutional practice.

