Subjects should be seen for all visits/assessments as outlined in the assessment schedule or as close to the designated day/time as possible. Missed or rescheduled visits should not lead to automatic discontinuation. Subjects who prematurely discontinue study treatment (ruxolitinib) for any reason should be scheduled for an end of treatment (EOT) visit within the time required per [Table 8-1](#), at which time all of the assessments listed for the EOT visit should be performed. At this End of treatment visit, all dispensed investigational product should be reconciled, and the adverse event and concomitant medications recorded on the eCRF. Subjects should then follow the early discontinuation follow-up visit schedule as described in [Section 8.2.1](#).

As per [Section 4.6](#), during a Public Health emergency as declared by Local or Regional authorities i.e. pandemic, epidemic or natural disaster that limits or prevents on-site study visits, alternative methods of providing continuing care may be implemented by the investigator as the situation dictates.

Table 8-1 Assessment Schedule

Period	Screening	Treatment Period Cycles 1-39, q28 day cycles								Safety Follow-up	Early Discontinuation Follow-up
Visit Name	Screening	Cycle 1				Cycle 2 - Cycle 6	Cycle 7	Cycle 9 - Cycle 39 (q 12 weeks)	End of treatment visit (EOT)	Safety Follow-up	Every 6 months until 3 years from first dose
Days	-28 to -1	1	8 (+/- 3d)	15 (+/- 3d)	22 (+/- 3d)	D1 each cycle (+/-7d)	Day 1 (+/- 7d)	D1 each cycle (+/-14d)	(+7d from last dose)	Last dose +30 days, (+3d)	Q 6 months (+/- 14d)
Prior/Concomitant Medications	X	X	X	X	X	X	X	X	X	X	
Non-drug therapy and procedures	X	X	X	X	X	X	X	X	X	X	
Physical Examination	S	S	S	S	S	S	S	S	S		
Height	X	X				X	X	X	X		X
Weight	X	X	X	X	X	X	X	X	X		X
Vital Signs	X	X	X	X	X	X	X	X	X		
Tanner staging (if not Tanner Stage 5 at Screening)	X							X (Annually)	X		X (Annually)
Laboratory Assessments	-										
Hematology	X	X	X	X	X	X	X	X	X		
Chemistry	X	X	X	X	X	X	X	X	X		
Hepatitis serology markers (HBV, HCV)	X										
Hepatitis viral load (HBV, HCV)	X	X					X (drawn every 6 months while on ruxolitinib)	X (drawn every 6 months while on ruxolitinib)	X		

Period	Screening	Treatment Period Cycles 1-39, q28 day cycles								Safety Follow-up	Early Discontinuation Follow-up
Visit Name	Screening	Cycle 1			Cycle 2 - Cycle 6	Cycle 7	Cycle 9 - Cycle 39 (q 12 weeks)	End of treatment visit (EOT)	Safety Follow-up	Every 6 months until 3 years from first dose	

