2. On-treatment period: from day of first dose of ruxolitinib to 30 days after date of last actual administration of assigned treatment.
3. ***post-treatment period***: starting at Day 31 after last administration of ruxolitinib.

Safety summaries (tables, figures) include only data from the on-treatment period with the exception of baseline data which will also be summarized where appropriate (e.g. change from baseline summaries). In addition, a separate summary for death including on-treatment and post-treatment deaths will be provided. In particular, summary tables for adverse events (AEs) will summarize only on-treatment events, with a start date during the on-treatment period (***treatment-emergent*** AEs).

However, all safety data (including those from the post-treatment period) will be listed and those collected during the pre-treatment and post-treatment period will be flagged. In analyses for the safety disclosure, all AEs collected in the post-treatment period will be included and reported separately.

Subjects who taper off ruxolitinib due to achieving a CR or PR continue efficacy and safety assessments until their EoT visit which may be only after Cycle 39 unless the subject discontinues from study earlier. Safety data from these patients collected after the last study drug intake date + 30 days and before EoT visit will not be included in any safety analyses based on the on-treatment period as defined above. Nevertheless, these data will be listed and flagged in all listings (AEs, lab, vital signs). Subject who tapered off ruxolitinib are identified as they have reason "responder" for ruxolitinib permanent discontinuation on the exposure CRF.

For subjects who tapered off study treatment and later re-started ruxolitinib treatment after a cGvHD recurrence, the on-treatment period is from date of first dose of ruxolitinib to very last dose + 30 days including the period without treatment, which are collected in the database as dose interruption. Safety data (e.g. AEs, labs) collected during this period without treatment will be included in the summary tables as treatment emergent events.

Windows for multiple assessments

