Date of discontinuation from end of treatment pages	No condition.
- cGvHD assessment date	Non-missing assessment.

Source data	Conditions
- any specific efficacy assessment date if available (e.g. graft failure assessment, hematologic disease relapse/progression assessment)	
Laboratory/PK collection dates/Biomarker collection dates	Sample collection marked as 'done'.
Vital signs date	At least one non-missing parameter value.
Assessment date of development information (e.g. tanner staging)	Evaluation is marked as 'done'.
Collection date of acceptability and palatability questionnaire	Assessment performed is "Yes".
Start/End dates of AE	Non-missing verbatim term

The last contact date is defined as the latest complete date from the above list on or before the data cut-off date. The cut-off date will not be used for last contact date, unless the patient was seen or contacted on that date. No date post cut-off date will be used. Completely imputed dates (e.g. the analysis cut-off date programmatically imputed to replace the missing end date of a dose administration record) will not be used to derive the last contact date. Partial date imputation is allowed for event (death)/censoring if coming from 'Survival information' eCRF.

The last contact date will be used for censoring of patients in the analysis of overall survival, failure free survival, non-relapse mortality, and malignancy relapse/recurrence.

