2.13 Other Exploratory analyses

Chronic GvHD recurrence following completion of a taper of ruxolitinib

This analysis is performed only for patients who taper off ruxolitinib due to achieving a CR or PR. These subjects will be identified as they have reason “responder” for ruxolitinib permanent discontinuation on the exposure CRF. It’s planned to do this analysis at time of final CSR and only if sufficient number of subjects with cGvHD recurrence after tapering off occurred.

Time to recurrence is defined as the time from completion of a taper of systemic therapy until cGvHD recurrence. Patients without event will be censored at the last contact date. Kaplan-

Meier method and the Kaplan-Meier curves as well as survival probabilities at appropriate time points will be presented with 95% confidence intervals ([Brookmeyer and Crowley 1982](#)).

In case of single subjects (less than 5 subjects) with cGvHD recurrence after tapering off, data will be reported in listing only.

Systemic corticosteroid-free response rate

Systemic corticosteroid-free response rate is defined as the proportion of subjects taking no systemic corticosteroid therapy since at least 1 month (i.e. time between date of last corticosteroid drug intake and response assessment data is ≥ 30 days) and demonstrating a complete response (CR) or partial response (PR), at any time post-baseline. Subjects who didn't receive corticosteroids at baseline and still not taking corticosteroids at time of response will be considered as corticosteroid-free responder. Initiation of any new systemic therapy after cGvHD flare or recurrence, regardless when, means treatment failure and the subject is considered as non-responder. The endpoint is similar to the primary endpoint ORR, but considers all subjects who could not taper off systemic corticosteroids as non-responder regardless if they are in CR or PR, and considers all response assessments up to End of Treatment of the subject or data cut-off date.

Systemic corticosteroid-free response rate and its 90% confidence interval will be presented based on all subjects in the FAS and by subgroup of treatment naive cGvHD vs SR-cGvHD.

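### Time to cGvHD recurrence after ruxolitinib taper is censored at last contact, so follow-up after the last cGvHD assessment counts as recurrence-free

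*SAP*

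**What the plan says.** **Recurrence analysis.** SAP 2.13 covers subjects who taper off ruxolitinib because of CR or PR, identified by the reason responder "for ruxolitinib permanent discontinuation on the exposure CRF". The analysis is a Kaplan-Meier estimate, and the censoring rule is "Patients without event will be censored at the last contact date". It is run "only if sufficient number of subjects with cGvHD recurrence after tapering off occurred"; with fewer than 5 such subjects only a listing is given.

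**Last contact date.** SAP Table 2-2 builds this from survival follow-up, drug and concomitant medication records, laboratory, PK and biomarker samples, vital signs, adverse events and other sources as well as cGvHD assessments. SAP 2.1.1 then states its use: "The last contact date will be used for censoring of patients in the analysis of overall survival, failure free survival", followed by non-relapse mortality and malignancy relapse. Recurrence is not named.

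**Duration of response.** Protocol 12.5.1 censors it at last contact. SAP 2.7.1 censors it at the last response assessment, provided no event occurred within 84 days after the last GvHD assessment. The SAP document history logs the change of definition.

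**Follow-up after stopping ruxolitinib.** Protocol section 3: "Subjects who discontinue ruxolitinib for any reason earlier than 39 cycles will be followed every 6 months until 3 years from their first dose". Protocol section 8: "Subjects who prematurely discontinue study treatment (ruxolitinib) for any reason should be scheduled for an end of treatment (EOT) visit", then the early discontinuation schedule. The protocol summary, 8.2.1 and 9.1.1 agree. For taper-off responders, protocol 6.1.5 says: "Subjects who taper off ruxolitinib and all immunosuppressive therapy due to achieving a CR or PR will continue to follow the currently assigned Visit" schedule, with all efficacy assessments and mandatory reporting of recurrence. SAP 2.1.1 says: "Subjects who taper off ruxolitinib due to achieving a CR or PR continue efficacy and safety assessments until their EoT visit", which may come only after Cycle 39.

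**The concern.** A Kaplan-Meier curve treats everyone at risk as someone whose event would be seen if it happened. A subject whose cGvHD was last assessed at month 8 after taper, and who has a laboratory sample or survival call at month 20, stays in the risk set for twelve months in which a recurrence might not be recorded. Missed events and inflated time at risk both make responses look more durable off drug.

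The sponsor has already removed this weakness from duration of response. Recurrence after taper is its off-drug counterpart, yet it keeps the old rule.

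The visit rules decide how much unassessed time there could be. Taper-off responders are recorded as permanent discontinuations, and that is the wording that triggers six-monthly follow-up in protocol 8.2.1 and 9.1.1. The assessments listed in 9.1.1 for that follow-up include no cGvHD assessment.

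**Working it through.** The plan gives no figure for this endpoint, so there is none to reproduce. The check has four steps.

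**1. Which follow-up rule applies to a taper-off responder?**

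| Source | Taper-off responder |
|---|---|
| Protocol summary, 3, 8, 8.2.1, 9.1.1 | Six-monthly visits; no exception for responders |
| Protocol 6.1.5 | Stays on the assigned schedule with efficacy assessments; only those stopping for other reasons go to early discontinuation follow-up (also 6.5.1.2) |
| SAP 1.1 | States both rules in consecutive sentences |
| SAP 2.1.1 | Efficacy assessments continue to an EoT visit that may follow Cycle 39 |

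The two sets cannot both hold for this group. The specific passages are clear, but the general ones do not refer to them.

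**2. Bias if some subjects are not assessed.** Let R be true 24-month recurrence, f the share contacted to month 24 without cGvHD assessment, and d the share of their recurrences captured another way. Under last-contact censoring:

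estimated recurrence = (1 − f)R + f·d·R = R[1 − f(1 − d)]

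The documents give no f, d or R. Assume 12-month recurrence of 15%, 30% or 45% with constant hazard. Then R = 1 − 0.85² = 27.8%, 1 − 0.70² = 51.0%, or 1 − 0.55² = 69.8%.

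| f | d | Factor | R = 27.8% | R = 51.0% | R = 69.8% |
|---|---|---|---|---|---|
| 0 | any | 1.00 | 27.8% | 51.0% | 69.8% |
| 0.25 | 0 | 0.75 | 20.8% | 38.3% | 52.3% |
| 0.5 | 0.5 | 0.75 | 20.8% | 38.3% | 52.3% |
| 0.5 | 0 | 0.50 | 13.9% | 25.5% | 34.9% |
| 1 | 0 | 0 | 0% | 0% | 0% |

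**3. What remains if everyone stays on schedule.** Scheduled assessments are 12 weeks apart, so take a gap of 84 days (84/30.4375 = 2.76 months) between last assessment and last contact. With monthly hazard h = −ln(1 − 12-month rate)/12 = 0.0135, 0.0297 or 0.0498, the chance that a subject still at risk recurs in the gap is 1 − exp(−2.76h) = 3.7%, 7.9% or 12.8%. This is a per-subject chance in the tail, not the bias of the whole curve.

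**4. Does censoring at last assessment cure it alone?** Not if later-reported recurrences still count. Assume 20 taper-off subjects, R = 13/36 = 36% (the adult figure in protocol 1.1.2.1.2, borrowed for illustration), f = 0.5 with no assessment after taper, and d = 0.5.

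- Events: 10 × 0.361 + 10 × 0.361 × 0.5 = 3.61 + 1.81 = 5.42.
- Last-contact censoring: 5.42/20 = 27%.
- Last-assessment censoring without an event window: the unassessed event-free subjects leave at once, giving 5.42/(10 + 1.81) = 46%.

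One rule is too low and the other too high, against a true 36%. An event window removes the late-reported events from the numerator as well.

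**The case against.** The strongest reply is that the documents do keep this group under assessment. Protocol 6.1.5, SAP 1.1 and SAP 2.1.1 all say so, and SAP 2.7.1 plans to use response data collected after ruxolitinib discontinuation. This stands. A reader might infer from the general passages that the plan removes taper-off responders from cGvHD assessment; the documents do not support that. Under the specific rules f is about 0.

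Nor is it right that recurrence can be seen only at a scheduled assessment. Protocol 6.1.5 makes its reporting mandatory, restarted ruxolitinib and new cGvHD treatment are recorded, and unscheduled assessments that change management or response are captured. So d is above zero, by an unknown amount.

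A reader might also see a gap for a responder off ruxolitinib but still on a CNI. Protocol 6.1.5.2 bars ruxolitinib taper until the subject is off corticosteroids and CNIs, so this should rarely arise. The ruxolitinib bullet in the same section names only corticosteroids, and the two statements should be reconciled.

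Three further points limit the concern:

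- The list of last-contact endpoints in SAP 2.1.1 is not stated to be exclusive, so omitting recurrence is an inconsistency rather than a contradiction.
- The 9.1.1 list may not be exhaustive. The cGvHD row of Table 8-1 was not readable in the text available and should be checked.
- The listing rule would often suppress a badly biased curve. With 20 subjects, 36% recurrence and d = 0, the binomial chance of 5 or more observed recurrences is 68%, 27% or 0.6% when 25%, 50% or 75% are unassessed.

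None of this justifies last contact as the censoring date. It limits how far the estimate could be wrong.

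**Conclusion.** The concern holds in a limited form. The censoring rule in SAP 2.13 counts unassessed time as recurrence-free, and the bias can only lower recurrence. If taper-off responders stayed on the assigned schedule, the effect is confined to the interval between last assessment and last contact. If some were moved to six-monthly follow-up, it scales with f(1 − d): none at f = 0, half the estimate lost at f = 0.5 and d = 0, a quarter lost at f = 0.5 and d = 0.5. These shares and the recurrence rates are assumptions. The 13/36 is relapse or progression after response in adults, not recurrence after taper in children.

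It would be too strong to say that the trial's evidence on durability is compromised. Duration of response is the secondary endpoint for that and is already censored at last assessment. The primary endpoint is untouched, and the affected analysis is an exploratory addition in the SAP.

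**What to change.** **In SAP 2.13:**

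- Censor time to recurrence at the last cGvHD assessment on or before the cut-off.
- Count a recurrence as an event only if it falls within 84 days after the last cGvHD assessment, as SAP 2.7.1 does for duration of response. Without this window the change would overstate recurrence (step 4 of the working).
- List later-reported recurrences separately.
- Report how many taper-off responders had cGvHD assessments after taper, so that readers can judge f.

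**In the protocol:** the general follow-up passages (summary, 3, 8, 8.2.1, 9.1.1) and section 6.1.5 contradict each other for taper-off responders and must be reconciled. Enrolment had ended by 17 September 2021, and 156 weeks from then is September 2024, close to the SAP date of 7 October 2024. Reconciling them will therefore mainly document which rule sites followed, because missed assessments cannot be recovered. That makes the SAP change the more useful one.

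**Cost:** a few sentences in the SAP before final lock and one count table. Some subjects are censored earlier, so the interval is wider, and some genuine recurrences move from the curve to the listing.

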2.14 Interim analysis

In order to summarize one year of safety data, in addition to the primary efficacy analysis, an interim CSR will be reported when all subjects have completed 1 year of treatment or discontinued earlier. The final analysis will be performed and the final CSR produced after all subjects have discontinued from the study. The same SAP will be used for both the interim and final analysis.

Since the data for the primary efficacy assessment, ORR at Cycle 7 Day 1, will already be final once all subjects have completed 6 months of treatment, and in this clinical trial it is not planned to test specific hypotheses related to the efficacy endpoint(s), but to provide estimates of efficacy endpoints, no alpha adjustment will be made for the analysis of the primary endpoint.

3 Sample size calculation

The sample size for the primary objective of measuring ORR at Cycle 7 Day 1 is approximately 42 subjects, regardless of age.

The sample size calculation is based on the ORR at Cycle 7 Day 1, and the calculation will consider the Saw-Toothed behavior of power waving for single binomial proportion using an exact method ([Chernick and Liu 2002](#)). Considering the response rate of children using corticosteroids is 30% to 50% ([Wolff et al 2011](#)), we assume the true ORR at Cycle 7 Day 1 of the study population is 70%, and therefore, a minimum sample size of 42 subjects would provide $>80\%$ probability to have a 90% CI with lower limit $\geq 50\%$. [Table 3-1](#) provides

estimates of the probability to have a 90% CI with lower limit $\geq 50\%$, minimum number of responders required and two-sided 90% Clopper-Pearson CIs for various sample sizes.

Table 3-1 Probability to have a 90% CI with lower limit $\geq 50\%$ and 90% confidence intervals for different number of subjects

Sample size	Minimum No. of responders	Response Rate	Probability to have a 90% CI with lower limit $\geq 50\%$	90% CI	
30	20	0.67	0.730	0.501	0.807
31	21	0.68	0.688	0.515	0.813
32	22	0.69	0.644	0.528	0.820
33	22	0.67	0.733	0.509	0.801
34	23	0.68	0.693	0.522	0.807
35	23	0.66	0.773	0.504	0.789
36	24	0.67	0.737	0.517	0.795
37	24	0.65	0.807	0.500	0.778
38	25	0.66	0.774	0.512	0.784
39	26	0.67	0.740	0.523	0.790
40	26	0.65	0.807	0.508	0.774
41	27	0.66	0.776	0.519	0.780
42	27	0.64	0.836	0.505	0.765
43	28	0.65	0.808	0.515	0.771
44	28	0.64	0.861	0.501	0.757
45	29	0.64	0.836	0.511	0.763
46	30	0.65	0.809	0.521	0.768
47	30	0.64	0.860	0.508	0.755
48	31	0.65	0.836	0.517	0.760
49	31	0.63	0.881	0.505	0.747
50	32	0.64	0.859	0.514	0.753

4 Change to protocol specified analyses

One exploratory analysis endpoints is added:

Chronic GvHD recurrence following completion of a taper of systemic therapy (see [Section 2.13](#)).

5 Appendix

